- 1.) Acupuncture will acutely benefit autonomic dysregulation in AD/ADRD subjects with AIA as indexed by reduced HRV and SC during treatment compared to pre-treatment rest.
- 2.) There will be a short-term benefit of acupuncture treatment on autonomic regulation as indicated by increased mean HRV and less motor restlessness on actigraphy and on behavioral symptoms as indicated by lower reported score on the Profile of Mood States (POMS)-abbreviated and fewer AIA symptoms documented by the subject or study partner during the observation period following the treatment compared to the pre-treatment observational day.
- 3.) Individuals without AIA, both CU and AD/ADRD, will reap similar benefits on autonomic regulation and behavioral symptoms as those with AIA.

III. SUBJECT SELECTION

Inclusion: Study subjects should meet all the inclusion criteria during screening evaluations to be entered into the study.

- Ages 55-95 inclusive, male or female.
- Diagnosis of CU, or probable AD, FTD or DLB as determined by established clinical criteria at screening¹⁴.
- For the AIA symptomatic groups, a score of > 2 for Severity on at least 1 of the AIA-relevant items on the NPI-Q, i.e., Anxiety, Irritability/Lability, Agitation or Aggression.
- For the CU and no neuropsychiatric symptoms group, NPI-Q score must be 0 for AIA-relevant items, i.e., Anxiety, Irritability/Lability, Agitation or Aggression.
- No concurrent use of therapies with prohibitive effects on interpretation of HRV and SC measurements, e.g., those with major direct adrenergic or anticholinergic activities.
- Stable doses (>2 weeks) of concurrent dementia or psychiatric drugs for those applicable.

Exclusion: Study subjects should not meet any exclusion criteria during screening evaluations or they will be excluded from entry into the study.

- Atrial or junctional arrhythmias or other cardiac conditions, including pacemakers or other implantable devices that affect RR intervals or their measurement.
- AIA symptoms or dementia so severe that subject cannot assent and cooperate with all study procedures or requires immediate rescue medication for behavioral control.
- Seizure disorders or other potentially confounding medical, neurological or longstanding psychiatric illnesses.

Subjects will be recruited from the parent AIA study. The parent study, “A Test-Retest Reliability Study of Non-Invasive Measures of Autonomic Nervous System Physiology and

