Should a subject agree to participate in the acupuncture sub-study, sign consent, but subsequently change their mind, they will not be punished. Signing consent for the sub-study will not bind the participant into receiving acupuncture treatment. Repealing consent will not affect participation in the parent study in any way. Similarly, should a subject wish to terminate the acupuncture treatment mid-session, the licensed acupuncturist will immediately remove the needles and ensure the subject is safe to return home.

This study will be conducted in compliance with Title 21 Part 50 of the United States of America Code of Federal Regulations (CFR), Federal Regulations, and ICH Guidance Documents pertaining to informed consent.

V. STUDY PROCEDURES

The sub-study will be introduced to subjects during the consenting process for the AIA parent study. It will be emphasized that participation in the acupuncture portion as a sub-study is strictly voluntary and will in no way affect participation or eligibility in the parent study.

After the second day of participation in the parent study, individuals who would like to participate in the sub-study will receive a 20-minute acupuncture session. Before beginning, participants will be asked to complete the POMS-abbreviated mood questionnaire. We will employ a modified standardized acupuncture protocol with points used in previous research studies¹⁰ to effectively reduce symptoms of anxiety and depression in individuals with dementia. The treatment will include commonly used acupuncture points for a total of 9 needles located on the top of the head, forehead, hand, wrist, lower leg, ankle and top of foot at approximately 0.5 – 1 cm depth. Needles will be placed at acupoints GV20 (x1), Yintang (x1) and left HT-7 (x1), left LI-4 (x1), right PC-6 (x1), bilateral ST- 36 (x2), right KD- 3 (x1) and left LV-3 (x1). A licensed acupuncturist credentialed by MGH will perform all acupuncture treatments. Upon insertion, the study acupuncturist will manipulate the needles to elicit the “de qi” sensation common in acupuncture treatments. Participants will then repeat the POMS-abbreviated shortly following the removal of acupuncture needles. Finally, participants will repeat the POMS a third time before removing the BioStamp nPoint the following day, roughly 20 ±4 hours after treatment.

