The data collected for this sub-study will consist of observed behavioral expression and reported AIA symptoms and mood, HRV, SC, and motor restlessness and actigraphy as measured by the BioStamp nPoint. Upon completing the parent study’s activities, subjects will remain connected to the SC measuring device, which will record SC throughout the acupuncture session. Additionally, subjects will wear the BioStamps home after completing the treatment. These will provide roughly 22 hours of HRV and actigraphy recordings post-acupuncture session. Finally, CU subjects or AD/ADRD study partners will be asked to complete a behavior diary. This will provide us with an understanding of the subjects’ behavior and symptoms for a day following acupuncture treatment. This diary will be returned via mail with the BioStamps and third POMS. Once these are received, data will be entered into the EDC and the participant will have completed the study.

VI. BIOSTATISTICAL ANALYSIS

General Considerations: Statistical analyses will begin with scatterplot inspection, and descriptive statistics. All variables will be checked for normality and other parametric assumptions, with appropriate transformation applied if necessary for parametric analyses. If normality assumptions cannot be met, non-parametric test equivalents will be used. Missing data, if any, will be characterized, with scrutiny towards identification of any patterns of missingness. Demographic and clinical characteristics of the sample will be evaluated and potentially important differences in these characteristics (e.g., age, sex, education, non-psychiatric medication class) by diagnoses will be assessed using χ^2 tests or Student t-tests (and/or ANOVA) for categorical and quantitative variables, respectively. Demographic or clinical variables that differ between groups will be included as covariates. $P < 0.05$ will be considered significant. This study is a pilot study, largely descriptive and exploratory. Multiple comparison corrections will not be applied in the primary analyses.

We hypothesize that the acupuncture will acutely benefit autonomic dysregulation in AD/ADRD subjects with AIA as indexed by reduced HRV and SC during treatment compared to pre-treatment rest. Therefore, we will explore any differences in HRV/SC after during/after treatment compared to pre-treatment rest.

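### Hypothesis 2 reads an unmatched, uncontrolled before-after change as a benefit of acupuncture; match the two windows and report the result as uncontrolled change

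*Combined protocol and SAP*

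**What the plan says.** Hypothesis 2 (section II, restated in section VI) names four measures: mean HRV, motor restlessness on actigraphy, the abbreviated POMS, and AIA symptoms recorded by the subject or study partner. Each is to improve "during the observation period following the treatment compared to the pre-treatment observational day", and the improvement is described as a short-term benefit of the treatment.

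Section V gives the timing:
- **Treatment:** "After the second day of participation in the parent study". No clock time is stated.
- **Sensors worn home:** "These will provide roughly 22 hours of HRV and actigraphy recordings post-acupuncture session".
- **First POMS:** "Before beginning, participants will be asked to complete the POMS-abbreviated mood questionnaire".
- **Third POMS:** "before removing the BioStamp nPoint the following day, roughly 20 ±4 hours after treatment".
- **Diary:** "CU subjects or AD/ADRD study partners will be asked to complete a behavior diary", to describe "behavior and symptoms for a day following acupuncture treatment".

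Section VI says that changes in these measures will be explored, with P < 0.05 called significant and no multiplicity correction in the primary analyses. Its only adjustment rule is "Demographic or clinical variables that differ between groups will be included as covariates". The study is labelled a pilot, largely descriptive and exploratory. The length and clock hours of the pre-treatment day are not given here. The parent study, cited by protocol number in section III, may give them.

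**The concern.** HRV and movement can both differ between sleep and waking. If the two windows hold different proportions of sleep, their means can differ with no treatment effect. The covariate rule concerns demographic or clinical differences between groups and cannot correct a difference between two windows in the same person.

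Order is a second problem. The treated period always comes after the parent study days, so habituation to sensors and procedures, or any other drift over days, falls entirely on the post-treatment side. No sham or untreated group is described. The groups do not fill that role: they differ by symptoms or diagnosis, and hypothesis 3 predicts similar benefit in people without AIA. A shift shared by all groups would look like support for hypothesis 3.

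For POMS and the diary, the comparison named in hypothesis 2 is not the one in section V. The POMS baseline is a single score just before needling, and the only diary described covers the day after treatment.

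**Working it through.** The plan states no sample size, SD or effect size, so there is no figure of its own to reproduce. What follows is an illustration.

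**Input from the documents.** Post-treatment window: roughly 22 h (section V).

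**Assumptions.** Comparator length T = 24, 20 or 16 h, or a 12 h daytime-only window. Sleep s = 8 h in every window except the daytime-only one (s = 0). Movement in sleep r = 0.1 to 0.3 of waking. HRV in sleep k = 1.1 to 1.5 times waking. No treatment effect.

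**Formulas.** Sleep share = s/T. Mean activity relative to waking = (T - s + s·r)/T. Mean HRV relative to waking = (T - s + s·k)/T. Shift = post/pre - 1.

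**Worked case, 24 h before and 22 h after.** Sleep share goes from 8/24 = 33.3% to 8/22 = 36.4%.
- Activity, r = 0.1: 16.8/24 = 0.700; 14.8/22 = 0.673; shift -3.9%.
- Activity, r = 0.3: 18.4/24 = 0.767; 16.4/22 = 0.745; shift -2.8%.
- HRV, k = 1.1: 24.8/24 = 1.033; 22.8/22 = 1.036; shift +0.3%.
- HRV, k = 1.5: 28/24 = 1.167; 26/22 = 1.182; shift +1.3%.

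| Comparator, against 22 h after | Activity shift | HRV shift |
|---|---|---|
| 24 h | -2.8 to -3.9% | +0.3 to +1.3% |
| 22 h, same clock hours | 0 | 0 |
| 20 h | +3.5 to +5.1% | -0.35 to -1.5% |
| 16 h | +15 to +22% | -1.3 to -5.5% |
| 12 h, daytime only | -25 to -33% | +4 to +18% |

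With 6 to 9 h of sleep, the 24 h row widens to -1.9 to -4.6% and +0.2 to +1.4%.

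**Effect on a test.** Let the sleep-minus-wake HRV difference be D standard deviations of the paired change. The spurious shift in SD units is (difference in sleep share) × D. For a two-sided paired z-test with n pairs and x = shift × √n, P(p < 0.05) = Φ(x - 1.96) + Φ(-x - 1.96). Assume D = 1 and n = 20:
- 24 h comparator: share difference 0.030, x = 0.13, P = 0.052.
- 12 h daytime-only comparator: share difference 0.364, x = 1.63, P = 0.37.

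Over D = 0.5 to 2 and n = 10 to 40, the ranges are 0.050 to 0.067 and 0.089 to 0.996.

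**Day order.** Nothing in the documents sizes it, and matched windows leave it untouched.

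**The case against.** The pre-treatment day appears to belong to the parent study, whose protocol would naturally define it and any pre-treatment diary. With a near-24 h comparator the window effect is trivial. The study calls itself exploratory, and section VI commits only to exploring changes; the benefit wording is a hypothesis. Day order is a limitation of any single-arm design.

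Much of this stands. Four stronger readings are tempting and are not supported:

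- **The comparator was never defined.** The documents show only that this plan does not restate it or point to where it is defined.
- **The windows will produce a false acupuncture effect.** The shift may be near zero, and a comparator shorter than 22 h that still contains the night shifts both measures against acupuncture.
- **Recordings may stop at 16 h.** That is the lower limit for the third POMS, taken before sensor removal. The stated recording length is roughly 22 h. If a recording did stop at 16 h against a 24 h comparator, activity would shift -15 to -21% and HRV +1.6 to +7.1%, but this is an edge case.
- **Section VI's remark that SDNN reflects variability over the recording epoch sizes the problem.** The plan does not say that the epoch is the whole window, and the calculation above concerns a time-weighted mean, not SDNN.

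What does not stand is that the pilot label or the parent protocol settles the matter. A parent definition would not put a matching rule or an untreated reference into section VI, and exploration does not by itself stop a before-after change from being credited to acupuncture.

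**Conclusion.** The point holds. Hypothesis 2 attributes a within-person change to acupuncture, while section VI neither matches the windows nor uses an untreated reference, in a fixed order. The window part is small if the pre-treatment day is close to a 24 h recording, and becomes material, in either direction, if it is short or daytime only. The documents do not say which applies, and the percentages rest on assumed sleep hours and sleep/wake ratios. The day-order part cannot be sized. POMS is exposed to day order and time of day but not to recording length. The change should be made because the remedy is cheap and limits what can be concluded; a large bias has not been shown.

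**What to change.** 1. **Windows.** Cite the parent protocol's definition of the pre-treatment day. For each person, compare HRV and actigraphy over the same clock hours and equal length in both windows, and keep the whole-window result alongside. Any sleep/wake split should be supplementary only: sleep may itself respond to treatment (the background lists sleep disorders among the conditions acupuncture is said to help), and the plan describes no sleep-scoring step.
2. **Reference and wording.** Where the parent test-retest study holds untreated repeat recordings of the same measure, report that day-to-day change (mean and SD) beside the post-treatment change. In all cases describe results as uncontrolled change after acupuncture and do not attribute them to it.
3. **Baselines.** State in hypothesis 2 that the POMS baseline is the score just before needling. Compare diary symptoms over equal periods only if a pre-treatment diary exists; otherwise describe them after treatment only.

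**Cost.** Wording, re-cutting of existing recordings, and discarded hours. If the clock hours otherwise overlap, about 2 h per person is lost with a 24 h comparator (24 - 22). With a shorter comparator the loss falls on the post-treatment side: 6 h at 16 h (22 - 16) and 10 h at 12 h (22 - 12). The parent reference is non-randomised, may not exist for every measure, and limits the day-order problem without removing it.

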In HRV analysis, more than 70 variables can be calculated in time- and frequency-domains,¹² including those mentioned previously: mean RR interval, SDNN, RMSSD, NN50 counts and three spectral frequency bands (very low, low and high) as well as total spectral power. In the time domain, SDNN reflects all the cyclic components responsible for variability in the recording epoch, so represents total variability. RMSSD is thought to reflect vagal tone and is relatively free of respiratory influences. In the frequency domain, low frequency (LF) band is thought to reflect a mix of sympathetic and vagal activity, while the high frequency (HF) band reflects vagal tone. The ratio LF/HF is often used as an index of overall sympathovagal balance. In SC analyses, resting tonic SC levels, non-specific skin conductance response (NS-SCR) amplitudes and frequencies occurring during tonic recording, and event-related skin conductance response (“ER-SCR”, as with acoustic startle or an emotional stimulus) are the common measures. NS-SCR frequency is often interpreted as reflecting background sympathetic arousal and startle ER-SCR as the event-related sympathetic arousal responsiveness. Our analysis will explore any differences in post-treatment HRV/SC compared to pre-treatment.

We also hypothesize that there will be a short-term benefit of acupuncture treatment on autonomic regulation and behavioral symptoms as indicated by increased mean HRV, less motor restlessness on actigraphy, lower reported score on the POMS-abbreviated, and fewer observational AIA symptoms documented by subject or study partner during the observation period following the treatment compared to the pre-treatment observational day. Therefore, any changes in these measurements will be explored.

VII. RISKS AND DISCOMFORTS

The risks associated with acupuncture are like any procedure that involves the insertion of needles through the skin. These include but are not limited to fainting, bleeding, infection, increased pain, nerve and tissue damage, needle breakage. None of these risks are common. The acupuncturists are fully trained and licensed and will take every precautionary measure to avoid any adverse effects.

VIII. POTENTIAL BENEFITS

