It is possible that some of the patients will derive direct benefit from participation in the acupuncture. If any patient wishes to continue acupuncture, the licensed managing acupuncturist will provide them with a list of competent and validated practitioners in their community.

Moreover, it is anticipated that findings from these studies will help advance brain research generally, and in understanding the possible benefits of acupuncture on AIA symptoms in AD/ADRD.

IX. MONITORING AND QUALITY ASSURANCE

The PI, [name], will ultimately be responsible for the validity and integrity of the data collected at the MGH site, and for ensuring that the study is conducted in accordance with the IRB-approved protocol. After data is collected and recorded on forms, the study coordinator may input the data into the Partners approved REDCap. Entries will be reviewed for accuracy and completeness by a second study coordinator. Finally, the PI or her designee (Co-I) will conduct monthly reviews to check that data in REDCap accurately reflects the data collected on the original data capture forms. The research team (PI, Co-I, research coordinators) will subsequently meet to discuss the results of this review, as well as case report forms and source documentation.

All electronic documentation will be stored on password-protected devices in locked cabinets located in secured areas. Paper forms will be stored in locked cabinets located in secured areas. [name] will ultimately be responsible for the accuracy of the data.

Subjects will be monitored for adverse events from the time they sign consent until completion of their participation in the study. For the purposes of this study, an adverse event (AE) will be defined as any unfavorable or unintended sign (including a clinically significant abnormal laboratory finding, for example), symptom, or disease temporally associated with the study. Stable chronic conditions (e.g. arthritis) that are present prior to the start of the study and do not worsen during the trial will NOT be considered adverse events. Chronic conditions that occur more frequently (for intermittent conditions) or with greater severity are considered as worsened and therefore would be recorded as adverse events.

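### The adverse-event window closes when mailed items are returned, and no active enquiry about harm is described after discharge, so later events may be under-ascertained

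*Combined protocol and SAP*

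**What the plan says.** Section IX (Monitoring and Quality Assurance) sets the period of safety observation: "Subjects will be monitored for adverse events from the time they sign consent until completion of their participation in the study". It defines an adverse event broadly, covering unfavorable signs, symptoms and diseases, and provides for review by the principal investigator and reporting to the ethics committee.

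Section V (Study Procedures) fixes when participation ends. Of the diary it says "This diary will be returned via mail with the BioStamps and third POMS", and then: "Once these are received, data will be entered into the EDC and the participant will have completed the study".

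Section V also describes what is collected after the session:

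- BioStamp recording at home for roughly 22 hours.
- A diary: "CU subjects or AD/ADRD study partners will be asked to complete a behavior diary". It is meant to show "behavior and symptoms for a day following acupuncture treatment".
- A third POMS, completed "before removing the BioStamp nPoint the following day, roughly 20 ±4 hours after treatment".

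The list of data in the same section reads: "The data collected for this sub-study will consist of observed behavioral expression and reported AIA symptoms and mood, HRV, SC, and motor restlessness". It names no adverse-event item.

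Section VII (Risks and Discomforts) lists the risks of needling: "These include but are not limited to fainting, bleeding, infection, increased pain, nerve and tissue damage, needle breakage". It calls none of them common and gives no rates or times of onset.

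**The concern.** Two features of the plan combine. First, the end of adverse-event monitoring is an administrative event, the arrival and entry of a mailed package, and not a set time after exposure. Two participants treated in the same way can be observed for different lengths of time for reasons unrelated to safety. Second, nothing described after discharge asks the participant or study partner about harm. The diary and the POMS serve the behavioral and mood outcomes.

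Some listed risks, such as fainting or needle breakage, would usually show themselves while the acupuncturist is present. Others, such as infection, increased pain, or nerve or tissue damage, can first show once the participant is home. For those the plan as written relies on what the one-day diary happens to record and on what is volunteered before the package is processed. Two things are at stake: a participant with a later complication may not come to the team's attention, and a count of no such events would not distinguish absence of harm from absence of enquiry.

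**Working it through.** The plan states no figure to reproduce here: no adverse-event rate, onset time or follow-up length. The check is a comparison of passages, with one piece of arithmetic on timing.

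**Step 1. When does the window close?** Section IX closes it at completion of participation. Section V puts completion at receipt and data entry of the mailed items. Together, the window closes when the mail has arrived and been entered. No minimum, maximum or default date is given for a participant whose items arrive late or not at all.

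**Step 2. When does scheduled collection end?** The third POMS is due at 20 ± 4 h:

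- earliest: 20 − 4 = 16 h after treatment
- latest: 20 + 4 = 24 h after treatment

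The diary covers a day and the BioStamps record for roughly 22 h. All described collection is therefore over about one day after treatment.

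**Step 3. How long might the formal window be?** Mail time is not stated. Assume 1 to 7 days (24 to 168 h) between completing the third POMS and receipt, with same-day data entry:

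- shortest: 16 + 24 = 40 h, about 1.7 days
- longest: 24 + 168 = 192 h, or 8 days

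The range ratio is 192 / 40 = 4.8. These limits only illustrate the variation; different assumptions about mailing would move both ends.

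**Step 4. Which instrument would detect each risk?**

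- During the session: the acupuncturist is present, so fainting, bleeding and needle breakage would usually be seen.
- First day at home: a diary of behavior and symptoms could pick up early pain or another symptom if the person completing it writes it down. The protocol describes no prompt for this.
- After the first day until the package is processed: the window is open, but no instrument, call, visit or form is described. An event counts only if someone volunteers it.
- After the package is processed: the window is closed.

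**Step 5. Can the shortfall be quantified?** With *n* participants, true probability *p* of an event first appearing after discharge, and probability *s* that such an event is recorded, the expected recorded count is *n* × *p* × *s*. The documents supply none of the three. In addition, *s* varies by participant because the window does. A recorded count of zero is compatible with a small *p*, a small *s*, or both, and the documents give no means of separating them.

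**The case against.** The strongest reply is that the plan's safety provisions are broader than this reading allows. The diary does record symptoms, and a symptom can meet Section IX's definition of an adverse event. For AD/ADRD participants the study partner completes it, which lessens the problem of self-report, and Section III excludes people whose dementia is too severe for them to cooperate. Outcome data and adverse events are handled in different sections, so the lack of an adverse-event item in the Section V list proves little by itself. The principal investigator is to monitor well-being closely, forms are checked by a second coordinator and reviewed monthly, and the diary would be handled at data entry, before completion. The intervention is one 20-minute session with nine needles, the study is a largely descriptive pilot, and no stated aim concerns safety or tolerability.

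Much of this stands, and it rules out several stronger readings:

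- A reader might infer that most later harms would be missed. The documents do not support this: no listed risk is labelled as delayed, no onset times or rates are given, the diary can capture first-day symptoms, and volunteered reports count until the window closes.
- A reader might infer that there is no contact after discharge. None is described in this protocol, but the parent protocol is not supplied and consent and contact pages were removed, so later contacts or reporting instructions may exist there.
- A reader might infer that the sample is mainly cognitively impaired. No group sizes are given, and cognitively unimpaired participants are enrolled.
- A reader might infer that a planned safety conclusion is invalid. The plan does not announce one.

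What the reply does not remove is the structure of the rule. The diary is not described as an adverse-event tool and stops after a day. The commitment to close monitoring gives no method or time point. Checking entries against source forms cannot find events that nobody asked about. The missing end date for someone who returns nothing is an administrative loose end; it lengthens the window and does not itself cause events to be missed.

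**Conclusion.** The concern holds in a limited form. As written, the adverse-event window depends on mail return and differs between participants, and this protocol describes no active enquiry about harm after discharge. Scheduled collection ends about a day after treatment. Section VII risks that appear later may be under-ascertained, and a zero count for them would be hard to interpret.

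The size of the effect cannot be computed. The firm figure is the 16 to 24 h timing of the last assessment; the span of roughly 1.7 to 8 days for the formal window rests on an assumed mail time of 1 to 7 days and same-day entry. The conclusion assumes that the parent protocol and consent form do not already supply a later enquiry; if they do, this protocol should refer to it. The point does not affect the efficacy analyses. It deserves a change because participant safety is involved and the remedy is small.

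**What to change.** In Section IX, replace the end point of adverse-event monitoring with a fixed interval from needle removal that does not depend on receipt of the mail. The investigator should set its length with the Section VII risks in mind; the documents give no basis for a particular number of days.

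At the end of that interval, have existing coordinator staff make one brief scripted enquiry to the participant, or to the study partner for AD/ADRD participants, that goes through the Section VII risks. Add the enquiry to the procedures and data list in Section V, and align the definition of completion there with the new window.

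State that the returned diary is reviewed for adverse events before the participant's record is closed.

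The cost is a short amendment, a brief form and about 10 minutes of coordinator time per participant. Completion will come slightly later, and a few more minor events may be recorded. Treatment and outcome measures are unchanged.
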